2.1.3 Exploratory Efficacy Objective

The exploratory efficacy objective for this study is to evaluate the efficacy of inavolisib plus palbociclib and fulvestrant compared with placebo plus palbociclib and fulvestrant on the basis of the following endpoints:

- Time to end of next-line treatment (proxy for time to second objective disease progression [PFS2]), defined as the time from randomization to end or discontinuation of next-line treatment, or death from any cause (whichever occurs first)
- Time to first skeletal-related event (SRE), defined as the time from randomization to the first occurrence of an SRE
 - A SRE is a pathologic fracture, radiation therapy to bone, cancer-related surgery to bone, or spinal cord compression.
- Mean and mean change-from-baseline scores in all functions (Physical, Role, Cognitive, Emotional, and Social), GHS/HRQoL, and disease- or treatment-related symptom scores, as measured by the scales of the EORTC QLQ-C30 and EORTC QLQ–Breast Cancer Module 23 Questionnaire (EORTC QLQ-BR23)

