Other local radiotherapy is not permitted with the following exception. It is understood that there may be circumstances requiring local radiotherapy in which the investigator does not believe that the symptoms are a result of disease progression (e.g., impending fracture) and the radiation field does not encompass a target/non-target lesion. In such cases, the patient should have a tumor assessment of the lesion(s) before they receive radiotherapy. If a patient received radiation therapy and a target or non-target lesion was included in the field of radiation, the lesion(s) will become unevaluable for tumor response.

Further reasons for avoiding local radiotherapy include the difficulty in distinguishing new symptomatic pain or worsening of lytic bone lesions from disease progression. Time-to-Deterioration in Pain is a secondary endpoint of this study and Time-to-First-Skeletal-related-Event is an exploratory endpoint; palliative radiotherapy may alter these results. As such, palliative radiotherapy to bone in the absence of disease progression may be allowed after consultation with the Medical Monitor, however, such patients will be censored from the aforementioned

secondary and exploratory endpoints. Few clinical data are available about potential toxicities of radiation and treatment with inavolisib. Study treatment should be held ~24 hours prior to palliative radiotherapy and until any effects or sequelae have resolved to Grade \leq 1. Patients should not miss more than one cycle of study treatment due to radiation treatment and must meet eligibility requirements to continue *in the* study treatment (Section 4.1.1). Previous clinical experience also suggests that new bone pain is frequently a symptom of disease progression. Bone pain secondary to fulvestrant treatment may be treated with pain medications, nonsteroidal anti-inflammatory drugs (NSAIDs), or corticosteroids.

- Primary prophylactic use of hematopoietic growth factors (e.g., erythropoietins, granulocyte colony-stimulating factor [G-CSF], and *granulocyte-macrophage colony-stimulating factor* is not permitted, however, they may be used to treat treatment-emergent neutropenia or anemia as indicated by the current ASCO guidelines or as secondary prophylaxis if dose reduction or delay is not considered a reasonable alternative.

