6. STATISTICAL CONSIDERATIONS AND ANALYSIS PLAN

The primary efficacy objective for this study is to evaluate the efficacy of inavolisib plus palbociclib and fulvestrant compared with placebo plus palbociclib and fulvestrant on the basis of PFS. The primary efficacy analysis population will consist of all randomized patients grouped according to their assigned treatment at randomization based on IxRS.

The safety analysis population consists of all patients who received at least one dose of study drug and is based on the treatment the patients actually received, that is, all patients who received at least one dose of inavolisib are included in the inavolisib plus palbociclib and fulvestrant group and all patients who received at least one dose of palbociclib and/or fulvestrant (and no inavolisib) are included in the palbociclib and fulvestrant group.

The primary analysis is triggered by the number PFS events required to achieve 85% power with 5% level of significance based on the assumptions outlined in Section 6.1. The 194 events are expected to have occurred *approximately 50* months after first patient randomized.

Method for type I error control of secondary endpoints, detailed list of planned sensitivity analyses and further additional information to the protocol are specified in the Statistical Analysis Plan (SAP). *The SAP may override the analyses as described in the study protocol, as applicable.* Details on the planned interim futility analysis and safety reviews are outlined in the iDMC charter.

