6.4.2.6 Patient- Reported Outcomes (TTD of Pain, PF, RF, and GHS/QoL)

To evaluate TTD in pain, the “worst pain” item from the BPI-SF will be assessed. TTD is defined as the time from randomization to the first documentation of a 2-point increase from baseline in “worst pain.” A 2-point change is defined as clinically meaningful (Mathias et al. 2010). Patients who do not have an observed deterioration at the time of the clinical data cutoff will be censored at the last non-missing assessment date. Patients without a post-baseline assessment will be censored at the time of randomization.

Time to deterioration in PF, RF, and GHS/ QoL will be assessed. TTD is defined as the time from randomization to the first documentation of a ≥ 10 -point decrease from baseline in the specific scale:

- Physical Function (items 1 through 5)
- Role Function (items 6 and 7)
- Global Health Status (GHS)/Quality of Life (QoL) (items 29 and 30)

Patients who do not have an observed deterioration at the time of the clinical data cutoff will be censored at the last non-missing assessment date. Patients without a post-baseline assessment will be censored at the time of randomization.

A ≥ 10 -point change is defined as a clinically meaningful difference (Osoba et al. 1998) on all scales of the EORTC-QLQ-C30.

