6.4.3 Exploratory Efficacy Endpoints

6.4.3.1 Exploratory Clinical Outcomes

- Time to end of next-line treatment (proxy for time to second objective disease progression [PFS2]), defined as the time from randomization to end or discontinuation of next-line treatment, or death from any cause (whichever occurs first). Data for patients without the occurrence of second objective disease progression or death and patients who have not started next-line treatment will be censored at the last date they were known to be alive. Data from patients without post-baseline information will be censored at the date of randomization. Analysis methodology is as outlined for the primary endpoint, PFS.
- Time to first SRE, defined as the time from randomization to the first occurrence of an SRE. An SRE is a pathologic fracture, radiation therapy to bone, cancer-related surgery to bone, or spinal cord compression. Data from patients without the occurrence of an SRE will be censored at the last valid visit. Data from patients without post-baseline information will be censored at the date of randomization. Analysis methodology is as outlined for the primary endpoint, PFS.

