1. INTRODUCTION

This Statistical Analysis Plan (SAP) provides details of the planned analyses and statistical methods for study WO41554 (INAVO120). For detailed information on the study, refer to the study protocol. The analyses described in this SAP will supersede those specified in Protocol WO41554.

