4.2.1 Definition of Primary Estimand

Following the estimand framework introduced in the ICH-E9 addendum (ICH 2020), the attributes of the estimand built around the primary endpoint are defined as follows:

- **Population:** patients with *PIK3CA*-mutant, hormone receptor (HR)-positive, HER2-negative locally advanced or metastatic breast cancer whose disease progressed during treatment or within 12 months of completing adjuvant endocrine therapy and who have not received prior systemic therapy for locally advanced or metastatic disease, as defined in study protocol (refer to Protocol Section 4.1)
- **Variable:** PFS, defined as the time from randomization to the first occurrence of disease progression as determined by the investigator and according to response evaluation criteria in solid tumors (RECIST) v1.1, or death from any cause (whichever occurs first)
- **Treatment:**
 - Experimental: inavolisib 9-mg tablet taken PO QD on Days 1–28 of each 28-day cycle, palbociclib 125-mg capsule or tablet taken PO QD on Days 1–21 of each 28-day cycle, and fulvestrant 500 mg administered by IM injection on Days 1 and 15 of Cycle 1 and then on Day 1 of each subsequent 28-day cycle
 - Control: placebo tablet taken PO QD on Days 1–28 of each 28-day cycle, palbociclib 125-mg capsule or tablet taken PO QD on Days 1–21 of each 28-day cycle, and fulvestrant 500 mg administered by IM injection on Days 1 and 15 of Cycle 1 and then on Day 1 of each subsequent 28day cycle
- **Intercurrent events and handling strategies:**
 - Start of non-protocol anticancer therapy prior to disease progression
 - Early discontinuation from study treatment for any reason prior to a PFS event
 - Handling ICE: Following treatment policy, the above ICE will be ignored and tumor assessment data collected after the ICE will be included in the primary PFS analysis
- **Population-level summary:** Hazard ratio for PFS

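### Protocol 4.4.3 censors patients for palliative bone radiotherapy in time to first SRE, although bone radiotherapy is itself a defined SRE

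*Protocol*

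**What the plan says.** Protocol 4.4.3 discourages local radiotherapy during treatment. One reason it gives is that time to deterioration in pain is a secondary endpoint, and that "Time-to-First-Skeletal-related-Event is an exploratory endpoint; palliative radiotherapy may alter these results". It then provides that palliative bone radiotherapy without progression "may be allowed after consultation with the Medical Monitor, however, such patients will be censored from the aforementioned" secondary and exploratory endpoints, meaning pain and SRE. It does not say at what date the patient is censored.

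Protocol 2.1.3 defines the event: "A SRE is a pathologic fracture, radiation therapy to bone, cancer-related surgery to bone, or spinal cord compression". Protocol 6.4.3.1 repeats the definition and adds: "Data from patients without the occurrence of an SRE will be censored at the last valid visit". Patients with no post-baseline information are censored at randomization. SAP 4.4 carries the same definition and the same censoring rule in almost the same words.

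On precedence, Protocol 6 says: "The SAP may override the analyses as described in the study protocol, as applicable". SAP 1 says: "The analyses described in this SAP will supersede those specified in Protocol WO41554", and the opening of SAP 4 repeats this.

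For pain, Protocol 6.4.2.6 censors patients who do not "have an observed deterioration at the time of the clinical data cutoff will be censored at the last non-missing assessment date". SAP 4.3.2.1 redefines the endpoint as time to confirmed deterioration (TTCD) and keeps that censoring rule. Neither section mentions radiotherapy.

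**The concern.** The same act has two opposite statuses. A patient irradiated for a bone lesion before progression has had an SRE under the endpoint definition, but is a censored observation under 4.4.3.

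If 4.4.3 were applied, time to first SRE would no longer measure what 2.1.3 describes. Palliative bone radiotherapy would count only when given at or after progression. Pre-progression radiotherapy, along with any later fracture or cord compression in the same patient, would drop out of the event count.

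The censoring would also be hard to defend as non-informative. Kaplan-Meier and Cox methods assume that a censored patient has the same future risk as those still under observation. A patient who has just needed bone radiotherapy is unlikely to meet that assumption. At stake are the SRE curves and hazard ratio, and whether two programmers working from these documents would produce the same dataset.

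**Working it through.** No arithmetic applies. The documents give no SRE rate, no bone radiotherapy rate and no expected event count for this endpoint. The check is a comparison of the texts.

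**Step 1. Status of palliative bone radiotherapy given without progression.**

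| Place | Status for time to first SRE | Date |
|---|---|---|
| Protocol 2.1.3 | Event, no exception | First occurrence, so the radiotherapy |
| Protocol 6.4.3.1 | Event; censoring only for patients with no SRE | As above; otherwise last valid visit |
| SAP 4.4 | Same as Protocol 6.4.3.1 | Same |
| Protocol 4.4.3 | Censored | None given |

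Three places agree and one contradicts them. The conflict already exists inside the protocol, before the SAP is consulted.

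**Step 2. Follow one patient.** Suppose a patient is irradiated for a painful bone metastasis with no progression, and later has a pathologic fracture. Under the definition, the event date is the radiotherapy. Under 4.4.3 there are at least three readings: censor at the radiotherapy date, censor at the last valid visit before it, or leave the patient out of the analysis. All three lose the radiotherapy event and the later fracture.

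**Step 3. Consequence for the comparison.** If such radiotherapy were less frequent in the inavolisib arm, the rule would remove more control events and tend to hide a benefit. If it were more frequent in that arm, the rule would remove more experimental events and flatter the drug. Nothing in the documents indicates which applies, so neither size nor direction can be stated.

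**Step 4. Does SAP precedence resolve it?** It points one way. SAP 4.4 gives an event list that includes bone radiotherapy and a censoring rule that does not mention it, and the SAP takes precedence. Two things keep this from being conclusive. First, SAP 4.4 nearly duplicates Protocol 6.4.3.1, and in the protocol that general text stood beside 4.4.3 as a specific exception. Repeating the general text does not show that the exception was considered and dropped. Second, the SAP never mentions palliative radiotherapy or 4.4.3.

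SAP 4.4 also takes its methodology from SAP 4.2.2, which brings in the intercurrent-event strategies of 4.2.1: "Following treatment policy, the above ICE will be ignored and tumor assessment data collected after the ICE will be included" in the PFS analysis. That leans the same way. But it is written for tumor assessments, and the SAP does not say whether palliative radiotherapy counts as non-protocol anticancer therapy.

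**Step 5. Pain.** Deterioration is defined by a questionnaire score, so radiotherapy is not part of the event and no event-versus-censoring conflict arises. SAP 4.3.2.1 states the event, how death and treatment discontinuation enter it, and who is censored and when. There is no radiotherapy step to apply.

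**The case against.** The strongest reply is that the SAP has already settled the matter. Its precedence statement covers the protocol's analyses generally. A rule on who is censored is an analysis rule wherever it appears, and SAP 4.4 is complete in itself. A general precedence statement exists so that each displaced clause need not be withdrawn by name. The affected group is also narrow: palliative bone radiotherapy, without progression, after discussion with the Medical Monitor, in a protocol that otherwise restricts local radiotherapy.

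Much of this stands. It makes counting the event the default reading, and it keeps the point minor. It does not remove the contradiction, because the protocol still gives the opposite instruction in specific terms and the SAP text that should displace it is the same general text the protocol already contained.

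A reader might go further and infer that the type I error-controlled pain test is also left undefined, since 4.4.3 names pain as well. The documents do not support that. The SAP has redefined the endpoint as TTCD, and 4.3.2.1 gives it a full censoring rule that takes precedence. Whether pain should be censored at palliative radiotherapy is a choice on which statisticians differ, and the SAP has made it by including no such step.

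**Conclusion.** Wrong as written, lowest severity, confined to an exploratory endpoint. Protocol 4.4.3 converts a defined SRE into a censoring and gives no date for it. The SAP's precedence favours treating the radiotherapy as an event but does not say so.

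The size is unknown and no estimate is offered. SRE carries no alpha. The 4.4.3 clause does not name PFS or OS, and no effect on them or on any alpha-controlled test is shown.

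The conclusion rests on reading the endpoint definition as meant literally, so that any radiation to bone counts. If the sponsor intended to exclude palliative radiotherapy given without progression, the definition in all three places would need changing instead, with a stated censoring date. Nothing in those sections suggests that intention.

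**What to change.** Add to SAP 4.4:

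> Any radiation therapy to bone, whether or not progression has been documented, is an SRE dated at the radiotherapy. The SRE censoring in Protocol Section 4.4.3 is not applied.

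Delete the censoring clause from Protocol 4.4.3 at the next amendment. Under Protocol 8.7 that edit needs IRB/EC approval and, where locally required, authority approval, so it need not be made on its own. The SAP text alone settles the analysis.

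For pain, no change is needed, because SAP 4.3.2.1 already governs. A sensitivity analysis censoring TTCD in pain at bone radiotherapy would answer the worry in 4.4.3 that radiotherapy may alter the result, but it is optional.

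The cost is two sentences. The radiotherapy dates should already be needed for the SRE endpoint, although the documents do not show the case report form. The change is best made before unblinding. The SAP was signed on 18 September 2023, and the documents do not show whether that was still possible. If it was not, the rule should be recorded as a clarification in the clinical study report.

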1.4.1 Clinical Pharmacokinetics of Palbociclib

The mean maximum concentration observed (C_{max}) of palbociclib is generally observed between 6 to 12 hours (time to reach maximum concentration) following oral administration. The mean absolute bioavailability of palbociclib after an oral 125-mg dose is 46%. In the dosing range of 25 to 225 mg, the area under the concentration-time curve (AUC) and C_{max} increased proportionally with dose in general. Steady state was achieved within 8 days following repeated once daily dosing. The geometric mean apparent oral clearance of palbociclib was 63.1 L/hr (29% *coefficient of variation*), and the mean (\pm standard deviation) plasma elimination half-life was 29 (± 5) hours in patients with advanced breast cancer.

Palbociclib absorption and exposure were very low in approximately 13% of the population under the fasted condition. Food intake increased palbociclib exposure in this small subset of the population, but it did not alter palbociclib exposure in the rest of the population to a clinically relevant extent. Therefore, food intake reduced the inter-patient variability of palbociclib exposure, which supports administration of palbociclib with food.

In vitro and in vivo studies indicated that palbociclib undergoes hepatic metabolism in humans. Following oral administration of a single 125-mg dose of [14 C]palbociclib to humans, the primary metabolic pathways for palbociclib involved oxidation and sulfonation, with acylation and glucuronidation contributing as minor pathways. Palbociclib was the major circulating drug-derived entity in plasma (23%). The major circulating metabolite was a glucuronide conjugate of palbociclib, although it only represented 1.5% of the administered dose in the excreta. Palbociclib was extensively metabolized, with unchanged drug accounting for 2.3% and 6.9% of radioactivity in feces and urine, respectively. In feces, the sulfamic acid conjugate of palbociclib was the major drug-related component, accounting for 26% of the administered dose. In vitro studies with human hepatocytes, liver cytosolic and S9 fractions, and recombinant SULT enzymes indicated that cytochrome P450 (CYP) 3A and SULT2A1 are mainly involved in the metabolism of palbociclib.

For more information, refer to the local prescribing information for palbociclib (i.e., package insert or SmPC).

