2. OBJECTIVES AND ENDPOINTS

This study will evaluate the efficacy, safety, and pharmacokinetics of inavolisib in combination with palbociclib and fulvestrant compared with placebo plus palbociclib and fulvestrant in patients with *PIK3CA*-mutant, HR-positive, HER2-negative locally advanced or metastatic breast cancer whose disease progressed during treatment or within 12 months of completing adjuvant endocrine therapy and who have not received prior systemic therapy for locally advanced or metastatic disease. Specific objectives and corresponding endpoints for the study are outlined below.

Throughout this protocol, "study drug" refers to any of the individual agents assigned to patients as part of this study (i.e., inavolisib, placebo, palbociclib, or fulvestrant), while "study treatment" refers to the combination of agents assigned to patients as part of this study (i.e., inavolisib plus palbociclib and fulvestrant, or placebo plus palbociclib and fulvestrant).

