4.4.3 Prohibited Therapy

Use of the following concomitant therapies is prohibited during the study and for at least 7 days prior to initiation of study treatment, unless otherwise specified below:

- Investigational therapy (other than protocol-mandated study treatment) is prohibited within 28 days prior to initiation of study treatment and during study treatment.
- Any concomitant therapy intended for the treatment of cancer (including, but not limited to, chemotherapy, hormonal therapy, immunotherapy, biologic therapy, radiotherapy, or herbal therapy) is prohibited for various time periods prior to starting study treatment, depending on the agent (see Section 4.1.2), and during study treatment, until disease progression is documented and the patient has discontinued study treatment.
- Hormone replacement therapy, topical estrogens (including any intra-vaginal preparations), megestrol acetate, and selective ER modulators (e.g., raloxifene) are prohibited unless required to treat adverse events.
- Quinidine or other anti-arrhythmic agents
- Radiotherapy for unequivocal progressive disease is prohibited, with the exception of new brain metastases in the setting of systemic response as follows: patients who have demonstrated control of their systemic disease (defined as having received clinical benefit [i.e., a PR, CR, or SD for ≥ 3 months]), but who have developed brain metastases that are treatable with radiation, will be allowed to continue to receive therapy with inavolisib/placebo, palbociclib, and fulvestrant *in the* study until they either experience systemic progression of their disease and/or further progression in the brain (based on investigator assessments). Treatment with inavolisib and palbociclib should be held at least 24 hours in advance of palliative radiotherapy and until any effects or sequelae have resolved to Grade 1 or better. Patients should not miss more than one cycle of study treatment due to radiation treatment and must meet eligibility requirements to continue *in the* study treatment (Section 4.1.1).

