- Strong CYP3A4 inhibitors, including, but not limited to, the following: atazanavir, ritonavir, indinavir, nelfinavir, saquinavir, clarithromycin, troleandomycin, itraconazole, ketoconazole, voriconazole, posaconazole, conivaptan, diltiazem, nefazodone, mibefradil, and grapefruit juice or grapefruit supplements. If co-administration of palbociclib with a strong CYP3A inhibitor cannot be avoided, reduce the dose of palbociclib as per palbociclib local prescribing information.
- Strong CYP3A4 inducers, including, but not limited to, the following: rifampin, carbamazepine, phenytoin, oxcarbazepine, phenobarbital, nevirapine, hyperforin (St. John's Wort), and cyproterone

The above lists of CYP3A4 concomitant medications are not necessarily comprehensive. Thus, the investigator should consult the prescribing information for any concomitant medication as well as the internet references provided below when determining whether a certain medication strongly inhibits or induces CYP3A4. Palbociclib local prescribing information should also be referred to for information on prohibited therapies and recommended dose adjustments for concomitant medications. In addition, the investigator should contact the Medical Monitor if questions arise regarding medications not listed above.

Drug Interactions Flockhart Table:

<https://drug-interactions.medicine.iu.edu/MainTable.aspx>

FDA Drug Interactions Table of Substrates, Inducers, and Inhibitors:

<https://www.fda.gov/drugs/drug-interactions-labeling/drug-development-and-drug-interactions-table-substrates-inhibitors-and-inducers>

Enrolled patients who subsequently require the use of any prohibited therapies must be discontinued from study treatment and followed for safety outcomes for 30 days after

their last dose of study treatment, or until they receive another anti-cancer therapy, whichever occurs first.

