4.6 TREATMENT, PATIENT, STUDY, AND SITE DISCONTINUATION

4.6.1 Study Treatment Discontinuation

Patients must permanently discontinue study treatment if they experience any of the following:

- Any medical condition that the investigator or Sponsor determines may jeopardize the patient's safety if she or he continues to receive study treatment
- Investigator or Sponsor determination that treatment discontinuation is in the best interest of the patient
- Intolerable toxicity related to study treatment determined by the investigator to be unacceptable given the potential for treatment benefit and the severity of the event
- Unequivocal disease progression per investigator assessment according to RECIST v1.1
- Symptomatic deterioration attributed to disease progression
- Non-compliance with protocol-specified drug administration and follow-up tests
- Concomitant use of any other (non-protocol) systemic anti-cancer therapy
- Pregnancy

The primary reason for study treatment discontinuation should be documented on the appropriate eCRF. Patients who discontinue study treatment will not be replaced.

All patients will return to the clinic for a safety follow-up visit 30 (± 7) days after the final dose of study treatment (see [Appendix 1](#) for additional details).

Discontinuation from final study treatment is not discontinuation from the study. After treatment discontinuation, information on survival follow-up and new anti-cancer therapy will be collected via telephone calls, patient medical records, and/or clinic visits, approximately every 3 months until death, unless the patient withdraws consent or the

Sponsor terminates the study. Patients that discontinue study treatment for reasons other than objective disease progression, withdrawal of consent, or death will continue to have tumor assessments performed every 8 weeks (± 7 days) for the first 2 years after randomization and then every 12 weeks (± 7 days) until documented disease progression or onset of new anti-cancer therapy, whichever occurs first.

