5.1.1.9 Drug–Drug Interactions

In vitro data suggest that inavolisib is metabolized by CYP3A4 and that there is a low-to-moderate potential for DDI with any medication that strongly inhibits or induces this enzyme. In addition, in vitro data suggest that inavolisib is a substrate of the efflux transporter P-glycoprotein. Palbociclib is extensively metabolized by CYP3A4. Co-administration of a strong CYP3A inhibitor (itraconazole) increased the plasma exposure of palbociclib in healthy subjects by 87%, and co-administration of a strong CYP3A inducer (rifampin) decreased the plasma exposure of palbociclib in healthy subjects by 85%. Therefore, strong CYP3A4 inhibitors and inducers are prohibited in this study (see [Section 4.4.3](#)).

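### The closing discontinuation order in Protocol Section 4.4.3 has no carve-out for uses the same section allows, such as an unavoidable strong CYP3A inhibitor with reduced palbociclib

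*Protocol*

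**What the plan says.** Section 4.4.3 of the Protocol opens by making its listed therapies "prohibited during the study and for at least 7 days prior to initiation of study treatment, unless otherwise specified below". Several of the items that follow then allow some use:

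- Hormone replacement, topical estrogens, megestrol and selective ER modulators may be used when needed to treat an adverse event.
- Patients with controlled systemic disease who develop brain metastases treatable with radiation may be irradiated and stay on all study drugs.
- Palliative bone radiotherapy without progression may be allowed after consulting the Medical Monitor, with dosing held and then resumed.
- Growth factors are barred as primary prophylaxis but allowed to treat neutropenia or anemia.
- For strong CYP3A4 inhibitors: "If co-administration of palbociclib with a strong CYP3A inhibitor cannot be avoided, reduce the dose of palbociclib as per palbociclib local prescribing information".

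The section ends: "Enrolled patients who subsequently require the use of any prohibited therapies must be discontinued from study treatment". Section 2 defines study treatment as a term that "refers to the combination of agents assigned to patients as part of this study", so the closing order covers all three drugs.

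Two other places bear on the point. Section 5.1.1.9 states: "Therefore, strong CYP3A4 inhibitors and inducers are prohibited in this study", and that sentence refers the reader back to Section 4.4.3. The mandatory discontinuation list in Section 4.6.1 has a single trigger tied to a concomitant drug: "Concomitant use of any other (non-protocol) systemic anti-cancer therapy".

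**The concern.** A patient whose strong inhibitor cannot be avoided is a patient who requires it. The bullet and the closing sentence therefore apply to the same person. The bullet reduces one drug, while the closing sentence stops three.

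The situation is foreseeable. The named inhibitors include clarithromycin, itraconazole, voriconazole and posaconazole, and Section 5.1.2.11 notes more infections with palbociclib combinations. At stake is the management of an individual patient. Someone who is neither progressing nor experiencing drug toxicity could lose the whole regimen because of an anti-infective course.

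A site in doubt has little help in the text. Section 4.4.3 offers the Medical Monitor for questions about medications it does not list, and these drugs are listed. Section 8.2 does not allow prospective requests to deviate. A site that reduces palbociclib departs from the literal closing order, and a site that discontinues departs from the bullet.

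**Working it through.** No arithmetic applies. The check sets the provisions of Section 4.4.3 side by side and asks what the closing sentence does to each.

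| Item in 4.4.3 | What the item allows | Closing sentence, read literally |
|---|---|---|
| Strong CYP3A4 inhibitor | Palbociclib reduced if the inhibitor is unavoidable | Stop all study drugs |
| Radiotherapy, new brain metastases | All study drugs continue | Stop all study drugs |
| Palliative bone radiotherapy without progression | Hold dosing, then resume | Stop all study drugs |
| Hormonal agents | Use to treat an adverse event | Stop all study drugs |
| Growth factors | Use to treat cytopenia | Stop all study drugs if growth factors count as prohibited |

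1. **Same patient?** Yes. Being unable to avoid a drug and requiring it are the same condition.
2. **Can both orders be followed?** No. A dose reduction has meaning only if palbociclib dosing goes on, and the closing order ends it.
3. **Does the lead-in resolve it?** Only by inference. Its qualifier attaches to the ban. The closing sentence reaches any prohibited therapy, uses the word must, and does not repeat the qualifier.
4. **Are the items equally exposed?** No. The hormonal and radiotherapy items state their exceptions as limits on the ban, and the growth-factor item bans only primary prophylaxis. Uses within those limits can fairly be called not prohibited. The inhibitor item is not worded that way: it bans the class and then gives a dose instruction. That is where the conflict is sharpest. Strong inducers have no dose-adjustment sentence, so for them there is no conflict.
5. **Do other sections decide it?** They lean one way without deciding. Section 4.4.1 sends sites to the palbociclib label for dose adjustments with concomitant medications, and Section 4.4.3 repeats that referral. Section 5.1.1.9 defers to 4.4.3. Section 4.6.1 does not list prohibited non-cancer drugs as a reason to stop. All of this fits dose reduction as the intended route. None of it limits the closing order.

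**The case against.** The strongest reply is that Section 4.4.3 is coherent when read as a whole. The closing order applies to prohibited therapies, and the ban that defines that class is subject to the in-item exceptions. If the order overrode those exceptions, it would also remove the brain-metastasis patients whom the section expressly keeps on treatment, which cannot be intended. The dose-reduction sentence would also have no purpose. On this reading the closing sentence covers only uses still prohibited after the exceptions.

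This stands as an account of intent. A reader might otherwise infer that the protocol issues two equal and opposite orders with nothing to choose between them, or that Section 5.1.1.9 imposes an independent ban without exception. The documents do not support either inference: the lead-in, the label referrals and the cross-reference in 5.1.1.9 all favor the exceptions. What the reply does not do is put the limit into the sentence that sites must follow, and the inhibitor bullet is the item least clearly framed as an exception.

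A reader might also take the 87% rise in palbociclib exposure with itraconazole (Section 5.1.1.9), together with the dose-proportionality described in Section 1.4.1, as showing that the reduction route is pharmacologically sound. That does not follow. The 87% comes from healthy subjects. The reduced dose is left to local prescribing information that the documents do not reproduce. Neither figure addresses inavolisib, which Section 5.1.1.9 describes as metabolized by CYP3A4 with low-to-moderate interaction potential.

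**Conclusion.** The point holds as a minor patient-management correction. Read literally, the closing sentence contradicts exceptions in its own section, most clearly for an unavoidable strong CYP3A inhibitor. The exceptions are probably meant to prevail. Per patient, the difference is three drugs stopped against one drug reduced.

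The number of patients is unknown. The documents give no rate of need for strong CYP3A inhibitors. The infection signal in Section 5.1.2.11 does not supply one, because it says nothing about whether other drugs would serve. With about 200 sites, mixed handling is possible but not shown.

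A reader might infer a threat to the primary analysis. The documents do not support that. SAP Section 4.2.1 handles early treatment discontinuation by treatment policy, and Protocol Section 4.6.1 continues tumor assessments after discontinuation until progression or new anti-cancer therapy. The trial is randomized and double-blind, and nothing suggests that handling would differ by arm. Inconsistent handling would mainly affect exposure and discontinuation summaries.

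The conclusion rests on two readings: that unavoidable and required describe the same patient, and that study treatment carries its Section 2 meaning in the closing sentence.

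**What to change.** Amend the closing sentence of Section 4.4.3 so that mandatory discontinuation applies to a prohibited therapy *other than a use permitted by an exception in this section*. Because the inhibitor bullet is not worded as an exception, it is safer to name it in that clause as an example: an unavoidable strong CYP3A inhibitor with palbociclib reduced.

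At the same time, the sponsor should confirm whether inavolisib/placebo continues unchanged, is reduced or is held during strong CYP3A inhibitor use, and state this in the bullet. That is a clinical pharmacology decision that the documents do not settle, and it should not be left to sites.

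The wording cost is one clause, plus a sentence on inavolisib/placebo. Eligibility and the analysis do not change. Section 4.3.2 already requires dose modifications to be recorded on the eCRF. Section 5.1.1.9 needs no edit because it already points to Section 4.4.3.
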